4.4.4 Exploratory outcomes

Exploratory outcomes of the study include the following:

- 4.4.4.1 Identification of antibody producing cells (APCs) from peripheral blood mononuclear cells (PBMCs), such as activated B cells and plasmablasts in patients before and during carfilzomib therapy, compared to LTRs without AMR and not receiving carfilzomib. This will be done using a combination of techniques including MHC class I and II tetramers, overlapping peptides to key MHC that are targeted by DSA responses, and an ELISPOT assay (so-called ex vivo studies).
- 4.4.4.2 Expansion of B cells from PBMC using a cytokine/anti-CD40 ligand cocktail as well as EBV transformation. We will then determine whether these B cell stimuli lead to detectable levels of in vitro alloantibody (compared to serum anti-HLA Abs detected by the HLA laboratory). Using carfilzomib in vitro, we will also determine whether it decreases the expansion of these APCs and blocks alloantibody production.

4.5 Safety plan

Patients will be enrolled according to the inclusion and exclusion criteria established in section 5.3. Patients will provide informed consent to participate in this clinical trial. In the informed consent process, patients will be educated about the purpose for carfilzomib and the potential adverse effects as described in section 6.1.1. Adverse effects will be recorded and graded according to the CTCAE as described above in section 4.4.3. Serious adverse effects (SAE) will be reported timely as required and established in section 6.4.

A study data safety monitoring board (DSMB) will be established consisting of 3 members who represent non-funded non-investigators with no conflicts of interest regarding carfilzomib or the IST funding agency. The study investigators will invite qualified individuals to participate in the DSMB. The DSMB members will possess either PharmD, PhD, or MD qualifications and have a working knowledge of lung transplantation and AMR. The DSMB will be chaired by one of the three members as determined by the DSMB membership. The DSMB will meet once yearly to review study progress, to ensure appropriate enrollment milestones are being met, and to review the adverse event reporting. The DSMB will meet on an ad-hoc basis to review any SAEs.

The DSMB may terminate the study only after at least 15 patients have been enrolled. The DSMB may only terminate the study for safety reasons in which the perceived risks of continuing to provide carfilzomib to upcoming patients who may be enrolled outweighs the potential benefit to the patient and the allograft. The DSMB may not terminate the study for any reason related to carfilzomib efficacy.

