4.1 Rationale

Carfilzomib is marketed for multiple myeloma and this IST represents an off label use of carfilzomib; thus, the criteria for phase II designation have been met. This prospective, open-label, single-arm active treatment trial will establish the rate of response to carfilzomib (in addition to conventional therapy) for AMR after lung transplantation. This information will be necessary for use in planning further larger dual-arm placebo or active therapy controlled clinical trials. This trial will enroll 30 patients at the University of Pittsburgh Medical Center. The volume of lung transplants performed and the rate of diagnosis of AMR at UPMC will allow for adequate enrollment of study patients within the 3-year study period.

The dosing strategy of carfilzomib will follow that of the multiple myeloma schedule as described below in section 5.3. This dosing strategy has been well-studied in patients with myeloma (see trial designations below) and has proven to result in an acceptable AE profile for the patients with AMR after lung transplantation. In addition, our preliminary off label experiences with this dosing strategy have yielded an acceptable AE profile in lung transplant recipients with AMR.

Trial designations:

Carfilzomib has been evaluated in 2 completed Phase 1 studies (PX-171-001 and PX-171-002), 5 completed Phase 1b/2 studies (PX-171-003, PX-171-004, PX-171-005, PX-171-006, and PX-171-008), and in 1 completed, Phase 2, expanded-access study (Study 2011-002, Carfilzomib Multiple Myeloma Expanded Access Protocol [C-MAP]) that was co-sponsored by Amgen and the Multiple Myeloma Research Foundation.

Carfilzomib is currently being evaluated in 2 ongoing Phase 1 studies (CFZ001 [Renal] and CFZ002 [Hepatic]), 5 ongoing Phase 1b/2 studies (PX-171-007, PX-171-010, 2012-002 [CHAMPION 1], 2012-003 [CHAMPION 2], and CFZ004 [small cell lung cancer]), 4 ongoing Phase 3 studies (PX-171-009 [ASPIRE], PX-171-011 [FOCUS], 2011-003 [ENDEAVOR], and 2012-005 [CLARION]), and 2 ongoing Phase 1/2 studies sponsored by Ono Pharmaceutical Co, Ltd in Japan (ONO-7057-01 and ONO-7057-02).

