5.9 Patient discontinuation

Patients will be removed from study continuation if the toxicities of therapy are deemed by the investigators to outweigh the potential benefit of therapy. Such toxicities may include severe thrombocytopenia (platelets < $10,000 \times 10^6$), acute kidney injury requiring renal replacement therapy, or severe hepatitis (ALT > 1000), or others deemed relevant to the individual patient by the investigators.

If patients discontinue study drug early, these patients may be replaced in the study by patients who are likely to complete at least 1 cycle of carfilzomib.

The investigators have the right to discontinue a patient from the study for any medical condition that the investigator determines may jeopardize the patient's safety if he or she continues in the study or if the investigator determines discontinuation is in the best interest of the patient.

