5.10 Study discontinuation

Amgen may discontinue the study prematurely for the following reasons: the incidence or severity of AEs in this study indicates a potential serious health hazard to patients, if enrollment is sufficiently poor, or if data recording is inaccurate or incomplete.

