7.4 Communication with the IRB

This protocol, the informed consent forms, and any information to be given to the patient must be submitted to the IRB by the co-principal investigators for review and approval before the study is initiated. In addition, any patient recruitment materials must be approved by the IRB.

The principal investigator is responsible for providing written summaries of the status of the study to the IRB at least annually in accordance with all IRB policies and procedures. Investigators are also responsible for promptly informing the IRB of any protocol changes or amendments and any unanticipated problems involving risk to patients or others.

Any other IRB requirements not delineated in this section must be fulfilled by the co-primary investigators.

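### The DSMB may not terminate the trial until 15 of 30 patients are enrolled (about month 18), although safety is its only permitted ground for terminating

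*Combined protocol and SAP*

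**What the plan says.** Section 4.5 (Safety plan) and the safety plan in the synopsis (section 1.3) set the same rule: "The DSMB may terminate the study only after at least 15 patients have been enrolled". The next sentence limits the ground: "The DSMB may only terminate the study for safety reasons", meaning that the risk of giving carfilzomib to future enrollees is judged to exceed the benefit. Efficacy is expressly excluded as a reason.

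Section 4.5 defines the board as three members who are "non-funded non-investigators with no conflicts of interest regarding carfilzomib or the IST funding agency". It meets once a year, and in addition "The DSMB will meet on an ad-hoc basis to review any SAEs".

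Other provisions bear on safety before patient 15:

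- Section 5.3.1.2 sets dose holds and reductions for individual patients.
- Section 5.9: "The investigators have the right to discontinue a patient from the study for any medical condition" that may jeopardise that patient's safety.
- Section 5.10 allows Amgen to discontinue the study if "the incidence or severity of AEs in this study indicates a potential serious health hazard to patients". No minimum enrolment applies.
- Section 7.4 requires the IRB to be told promptly of "any unanticipated problems involving risk to patients or others".

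The documents do not say whether the DSMB may pause enrolment.

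**The concern.** The board is asked to weigh risk against benefit for patients not yet enrolled, and must convene whenever an SAE calls for it. Yet during the first half of enrolment, when the largest number of patients is still to come, it cannot act on its own conclusion by terminating. If early SAEs convinced it that the risk was too high, it would have to leave termination to Amgen or others, or wait for patient 15.

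A minimum enrolment can make sense where a board might otherwise stop early on unstable efficacy or futility data. That reason does not apply here. Efficacy stopping is already barred, section 5.13 analyses the data only at study conclusion, and section 5.13.3 bases the sample size on expected accrual with no power calculation.

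Section 4.1 says that preliminary off-label experiences "have yielded an acceptable AE profile in lung transplant recipients with AMR". That is reassuring background, but it does not replace independent authority to stop the trial if its own data point the other way.

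**Working it through.** **Inputs.** Enrolment of 30 (synopsis, section 4.1); accrual of 10 per year for 3 years (section 5.13.3); floor of 15 (section 4.5 and synopsis); yearly plus ad hoc DSMB meetings (section 4.5).

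**The plan's own figure.** 10 per year × 3 years = 30, which reproduces the stated enrolment.

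**Length of the restriction.**

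- Share of enrolment: 15 / 30 = 50%.
- Time to patient 15: 15 / 10 × 12 = 18 months of 36.
- Assumed slower or faster accrual: 15 / 7.5 × 12 = 24 months; 15 / 12.5 × 12 = 14.4 months.
- If yearly meetings fall at months 12, 24 and 36 after first enrolment (an assumption; the protocol says only yearly), about 10, 20 and 30 patients are enrolled. The first meeting then has no power to terminate, and the first scheduled meeting that has it comes at about 20 patients.

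**Further enrolment before the board could act.** If the board were convinced after patient *k*, 15 − *k* more patients would have to enrol first. For *k* = 5 that is 10 patients, or 10 / 10 × 12 = 12 months. For *k* = 10 it is 5 patients, or 6 months.

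**Could concerning events accumulate by then?** The documents give no event rate for this population and no count that would trigger stopping, so the rates and the thresholds of 2 and 3 are illustrative. With X ~ Binomial(n, p):

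P(X ≥ 2) = 1 − (1 − p)^n − n p (1 − p)^(n−1)

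P(X ≥ 3) also subtracts [n(n−1)/2] p² (1 − p)^(n−2).

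Two values of n are used. The first is 14, the patients enrolled before the floor is reached. The second is 12, the patients past day 90 when patient 15 enrols. With even accrual there is one patient per 365 / 10 = 36.5 days, so patients 14, 13 and 12 are then at 36.5, 73 and 109.5 days, and patients 1 to 12 are past day 90.

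| Assumed rate p | n = 14, P(≥2) | n = 14, P(≥3) | n = 12, P(≥2) | n = 12, P(≥3) |
|---|---|---|---|---|
| 5% | 15.3% | 3.0% | 11.8% | 2.0% |
| 10% | 41.5% | 15.8% | 34.1% | 11.1% |
| 20% | 80.2% | 55.2% | 72.5% | 44.2% |
| 30% | 95.3% | 83.9% | 91.5% | 74.7% |

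For scale, the table in section 6.1.4, drawn from earlier carfilzomib trials in a different population, lists serious acute kidney injury at 4.4% and serious pneumonia at 9.7%. With n = 14 these give P(≥2) = 12.4% and 40.0%, and P(≥3) = 2.2% and 14.8%.

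**Who can do what before patient 15.**

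| Body | Power before patient 15 | Section |
|---|---|---|
| DSMB | Reviews SAEs; may not terminate; pausing not addressed | 4.5 |
| Investigators | Hold or reduce doses; withdraw individual patients | 5.3.1.2, 5.9 |
| IRB | Is told of unanticipated problems | 7.4 |
| Amgen | May discontinue the study for adverse events | 5.10 |

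The company that supplies the drug (section 7.7) may halt the study for safety from the first patient. The board defined as conflict-free may not.

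**The case against.** The strongest reply is that the trial can be stopped before patient 15. Amgen may discontinue it for adverse events without any floor, the DSMB sees SAEs as they arise, the IRB is informed, and individual patients are protected by dose holds and withdrawal. What remains is a question of who holds the authority. This is right as far as it goes, and it limits the claim: the gap concerns the DSMB's power and does not leave the trial with no way to stop. It does not close the gap, because none of these routes gives that power to the board.

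Other points stand in part:

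- The investigators invite the DSMB members, so its independence should not be overstated. It is still the only body the protocol expressly defines as non-investigator and conflict-free.
- The floor may have been meant to prevent termination on a chance cluster in very ill patients. The table above shows that such clusters are common at moderate rates. The documents do not give this reason, and it would support careful review of early events, not an absolute bar.
- The binomial figures show how often events would occur, not how often a board would decide to stop. They are the same with or without the floor, so the finding does not rest on them.
- Sections 4.5 and 5.10 govern different bodies. Their different conditions are not a strict contradiction, and linking the two sections is a drafting improvement.

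**Conclusion.** The concern holds. As written, the plan withholds the DSMB's only stopping power, which is confined to safety, for 15 of 30 enrolments, with no exception. That part follows from the text alone. The timing of about month 18 assumes the planned 10 patients per year; at 7.5 to 12.5 per year it would be month 24 to month 14.4. The event probabilities rest on assumed rates and thresholds and serve only as scale. Because the restriction bears directly on patient protection, serves no stated purpose and is easy to remove, it should be corrected.

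**What to change.** In section 4.5 and in the synopsis:

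- Delete the sentence that sets the 15-patient minimum.
- State that the DSMB may pause or terminate enrolment for safety at any time, including at an ad hoc SAE review.
- Keep its existing power to terminate, without reducing it to a recommendation, and keep the bar on stopping for efficacy.

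Add a cross-reference between sections 4.5 and 5.10 so that both name everyone who may halt the study for safety.

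The cost is one sentence changed in two places and one cross-reference. No dose, clinical rule or numerical stopping boundary is involved. The downside is that the trial could end with fewer than 15 patients, and only for a safety reason.

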4.6 Ethical considerations

There are no identifiable ethical considerations that would preclude the execution of this clinical trial. Patients cannot receive placebo since this IST represents a single-arm active-treatment trial.

4.7 Administrative structure

The Division of Pulmonary, Allergy, and Critical Care Medicine within the University of Pittsburgh School of Medicine employs substantial research infrastructure to successfully execute this IST. This infrastructure constitutes the UPMC Pulmonary Research Core. Working with the University of Pittsburgh Office of Research who will coordinate the expenditure of research funds and the execution of trial contracts, the research core will be responsible for all clinical trial interventional and regulatory support.

4.7.1 UPMC Pulmonary research core

The UPMC Pulmonary Research Core will be responsible for the support of this IST. The research core study coordinator will be alerted by one of the investigators of a patient who will be enrolled in the study. This coordinator will execute all paperwork required for enrollment in the clinical trial, establish patient linkage codes, support the data collection required by the IST, and collect any study blood obtained outside the routine clinical care of the patient, such as blood for PBMC isolation to support the exploratory outcomes.

4.7.2 Data management plan

All study data will be collected using REDcap. The pulmonary research core study nursing staff will be responsible for entering all data to be collected as required by this IST. This database will only contain linkage codes to identify the study patients. A separate file containing the protected health information of the study participants along with their linkage codes will be maintained. These files will be stored on secured research servers behind the University of Pittsburgh's research firewall. Data will only be accessible by protected passwords by study investigators and support personnel.

4.7.3 Investigational drug pharmacy

All study drug will be prepared and dispensed by the University of Pittsburgh Investigational Drug Service in accordance with the drug handling and dispensing practices outlined in appendix C. The investigational drug service charges a dispensing fee associated with each dose in the drug cycle. This fee is included in the study budget.

4.8 Compliance with laws and regulations and the institutional review board

This study will be conducted in accordance with the U.S. Food and Drug Administration (FDA) regulations, the International Conference on Harmonisation (ICH) E6 Guideline for Good Clinical Practice (GCP), and all applicable local, state, and federal laws.

This study will undergo full prospective institutional review board (IRB) evaluation by the University of Pittsburgh IRB prior to any patient enrollment to ensure scientific merit and all appropriate patient protections and information protections are in place.

5 Materials and methods

Patients 5.1

5.1.1 Patient selection

Patients will be eligible for enrollment if they have met the diagnostic criteria for AMR as described in section 4.3.6. This involves the identification of DSA via Luminex SAB technology prior to day 1. Any patient who meets the diagnostic criteria after study initiation will be screened for enrollment. Patients who satisfy the inclusion and exclusion criteria will be approached to provide informed consent and enroll in the study.

A 1:1 retrospective control group including lung transplant recipients from the University of Pittsburgh with Antibody Mediated Rejection will be created to describe differences in the endpoints using the CFZ-based regimen vs. historic standard of care.

5.1.2 Inclusion criteria

Adult lung transplant recipients ≥ 18 years of age who meet the diagnostic criteria for AMR as described in 4.3.6 who have underwent PFT testing unless intubated and transbronchial biopsy prior to enrollment. Patients who have not experienced improvement or regression are candidates for a second cycle of therapy on the protocol.

5.1.3 Exclusion criteria

Study exclusion criteria are as follows:

5.1.3.1 Exclusion related to disease

Direct contraindications or previous intolerances to any component of the standard of care regimen including PLEX, 5% human albumin, 5% gammagard S/D or 10% gammagard liquid

5.1.3.2 Exclusion related to general health

Leukopenia defined as WBC < 2000 Neutropenia defined as ANC < 1000 Thrombocytopenia defined as platelets < 75000 x 10⁶ Known Child-Pugh B/C cirrhosis Total bilirubin > 4 ALT > 90 Known systolic heart failure with LVEF < 40%

Known pulmonary hypertension

Any uncontrolled comorbid condition

Pregnant women (negative serum pregnancy test required within 7 days prior to study drug administration for women of childbearing potential)

Breastfeeding women

5.1.3.3 Exclusion related to risk for infections

Ongoing bacterial or fungal or viral infection that is life-threatening Active cytomegalovirus disease

Active varicella zoster infection

5.1.3.4 Exclusion related to medications

Previous intolerance to carfilzomib Concurrent use of another proteasome inhibitor (e.g., bortezomib)

5.2 Treatment assignment

This is an open-label single-arm active-treatment study; thus, patients will be assigned to carfilzomib therapy in the order in which they are enrolled.

5.3 Study treatment

Conventional therapy for AMR: Therapeutic plasma exchange (PLEX) 1.5 plasma volumes replaced with 5% albumin or fresh frozen plasma for 8 sessions every-other day. Total intravenous immunoglobulins (IVIG) 100 mg/kg IV after each PLEX with the exception of the final PLEX where IVIG 500 mg/kg will be given. On day 16, if the IgG level is below 700 mg/dL, an additional dose of IVIG 500 mg/kg will be administered. If the IgG result is found to be 700ml/dL or higher, the IVIG 500mg/kg dose will not be administered. Premedications will be given for IVIG as follows: acetaminophen 650 mg PO and diphenhydramine 25 mg PO both at least 30 minutes prior to and not more than 6 hours before IVIG, unless otherwise directed on the part of one of the investigators if believed to be in the best interests of patient care. On days where IVIG and CFZ are given together, only one set of premedications will be administered. Conventional therapy requires an inpatient hospital stay. Patients will receive a tunneled PLEX catheter and peripherally inserted central catheter (PICC) inserted by interventional radiology in the routine clinical care of these patients prior to receiving any conventional or carfilzomib therapy.

Conventional therapy rationale: PLEX serves two important roles in this regimen: first, to remove circulating injurious DSA, and second, to turn on the plasma cell apparatus due to depletion in order to enhance selection of highly active cells by the proteasome inhibitor. IVIG also serves two purposes: first, to provide putative Ig replacement to decrease infectious complications from PLEX, and second, to blunt the rebound antibody response due to depletion. Investigational carfilzomib will be given to enrolled patients between PLEX and IVIG on PLEX days, and alone on non-PLEX days. The rationale to insert carfilzomib between PLEX and IVIG is to avoid any derangements to the Fc γ receptor (Fc γ R) by IVIg and allow carfilzomib unfettered access to the highly active plasma cells.

5.3.1 Investigational therapy

Carfilzomib (in addition to conventional therapy). Please refer to appendix D, investigators brochure for additional information regarding carfilzomib and clinical trial data.

5.3.1.1 Dosage, administration, and storage

Carfilzomib dosing schedule: Carfilzomib will be administered on the multiple myeloma schedule consisting of 20 mg/m² on days 1 2, 8, 9, 15, and 16 (one cycle) to constitute one therapeutic cycle. On PLEX/IVIG days, carfilzomib will be given in between PLEX and IVIG to avoid inadvertent blockade of the Fcγ receptor. Carfilzomib will be delivered via central access IV over 30 minutes (+15 minutes); slowed to 60 minutes (+15 minutes) if infusion reactions occur.

Carfilzomib will be diluted in a total of 80 mL dextrose 5% water (D5W) for administration. Premedications for carfilzomib administration will be given as follows: acetaminophen 650 mg PO, diphenhydramine 25 mg PO, ondansetron 4 mg PO, prednisone 40 mg PO or methylprednisolone 40 mg IV, all at least 30 minutes prior to and not more than 6 hours before carfilzomib, unless otherwise directed on the part of one of the investigators if believed to be in the best interests of patient care. Preinfusion hydration with a one-time bolus of 250 mL 0.9% sodium chloride will be given at least 30 minutes prior to and not more than 6 hours before carfilzomib to minimize the nephrotoxic AE. Postinfusion hydration with a one-time bolus of 250 mL 0.9% sodium chloride may be given immediately after carfilzomib to minimize the nephrotoxic AE

Carfilzomib may be administered for 1-2 complete cycles in the study. A second cycle may be given for lack of resolution of AMR or for continued detection of DSA in the absence of allograft improvement. If > one cycle is needed, the patient must still meet the enrollment criteria prior to the second cycle, and must not have had improvement after the first cycle or have experienced regression from initial improvement to qualify for a second study cycle. If > two cycles are desired, these must be given outside of the study. If > two cycles are desired, the third cycle must not be given within 90 days of day 1 of the first cycle. If the third cycle begins within this 90 day period, this will constitute a protocol violation.

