1.3 PROTOCOL SYNOPSIS

TITLE: Combination Therapy with the Proteasome Inhibitor

Carfilzomib for the Antibody-Mediated Rejection Diagnosis in

Lung Transplantation Trial (PICARD-Lung)

Protocol number: PRO15010152

Study drug: Carfilzomib (Kyprolis®)

Phase: phase II

Patient enrollment: 30

Indication: Antibody mediated rejection after lung transplantation

Sponsor: [name]

DATE: 09/20/2018

Objectives

1: To test the hypothesis in a prospective interventional clinical trial that addition of carfilzomib to conventional therapy will result in depletion of the immunodominant DSA.

- 2: To test the hypothesis in a prospective interventional clinical trial that addition of carfilzomib to conventional therapy will result in improved or stabilized allograft function.
- 3: To test the hypothesis that lung transplant recipients with AMR have effector B cell/plasma cell populations that can be identified and characterized, and that carfilzomib alters these immune mechanisms.

Study design

Phase II, prospective, open-label, single-arm active treatment, single center pilot clinical trial of the addition of carfilzomib to conventional therapy for AMR after lung transplantation.

Outcome measures

Primary endpoint: absolute change in DSA strength, titer, and complement fixation from day 1 to day 42.

Secondary endpoints:

Absolute change in DSA strength, titer, and complement fixation from day 1 to day 90 and from day 42 to day 90

Absolute change in forced expiratory volume in 1 second (FEV1) from day 1 to day 42 and to day 90.

Presence or absence of pathologic changes consistent with AMR on transbronchial biopsy from day 1 to day 42.

Patient death at any time after day 1 attributable to AMR.

Safety endpoints:

Non-lung irreversible end-organ failure (e.g., end-stage renal disease) any time after day 1 attributable to carfilzomib.

Incidence of adverse effects (AE) requiring dose-modification any time during days 1-16.

Incidence of any AE at any time after day 1 as graded by the NIH Common Terminology Criteria for Adverse Events (CTCAE) (appendix B) criteria.

Incidence of hypogammaglobulinemia any time after day 1.

Incidence of culture-proven *de novo* infection any time after day 1.

Diagnosis of systemic inflammatory response syndrome (SIRS) any time during days 1-16

Patient death at any time after day 1 to day 90 attributable to carfilzomib.

Retrospective control group:

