4.4.3 Safety outcomes

Safety outcomes of the study include the following:

- 4.4.3.1 Non-lung irreversible end-organ failure (e.g., end-stage renal disease) any time after day 1 attributable to carfilzomib.
- 4.4.3.2 Incidence of adverse effects (AE) requiring dose-modification (see section 5.3.1.2) any time during days 1-16.
- 4.4.3.3 Incidence of any AE at any time after day 1 as graded by the NIH Common Terminology Criteria for Adverse Events (CTCAE) (appendix B) criteria, as follows:
 - Grade 1: Mild; asymptomatic or mild symptoms; clinical or diagnostic observations only; intervention not indicated.
 - Grade 2: Moderate; minimal, local or noninvasive intervention indicated; limiting ageappropriate instrumental ADL (Instrumental ADL refer to preparing meals, shopping for groceries or clothes, using the telephone, managing money, etc.).
 - Grade 3: Severe or medically significant but not immediately life-threatening; hospitalization or prolongation of hospitalization indicated; disabling; limiting self-care ADL (self-care ADL refer to bathing, dressing and undressing, feeding self, using the toilet, taking medications, and not bedridden).
 - Grade 4: Life-threatening consequences; urgent intervention indicated.

Grade 5: Death related to AE.

- 4.4.3.4 Incidence of hypogammaglobulinemia any time after day 1.
- 4.4.3.5 Incidence of culture-proven *de novo* infection any time after day 1.
- 4.4.3.6 Diagnosis of systemic inflammatory response syndrome (SIRS) any time during days 1-16; requiring at least 2 of the following 4 criteria:

Body temperature: < 36 or > 38 degrees Celsius

Tachycardia: > 90 beats per minute

Tachypnea: > 20 breaths per minute

White blood cells: < 4000 or > 12000 cells/mm³

- 4.4.3.7 Patient death at any time after day 1 attributable to carfilzomib.
- A 1:1 retrospective control group including lung transplant recipients from the University of Pittsburgh with Antibody Mediated Rejection will be created to describe differences in the endpoints using the CFZ-based regimen vs. historic standard of care.

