5.13.1 Analysis of the conduct of the study

Enrollment, protocol violations, and discontinuations from the study will be summarized by patient.

Demographic and baseline characteristics will be summarized using means, standard deviations, medians, interquartile ranges. All summaries will be presented by group.

Study drug administration data will be listed by dose level, and any dose modifications will be flagged. Means and standard deviations will be used to summarize the total dose of carfilzomib received. All summaries will be presented by group.

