5.13.2 Safety analyses

All AE data will be listed by patient, cycle, and dose. All AE occurring after informed consent is given will be summarized by event, system, and grade. All SAE will be listed and summarized separately.

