6.1.2 Adverse effect (AE) definition

An AE is any unfavorable and unintended sign, symptom, or disease temporarily associated with the use of an investigational medicinal product or other protocol-imposed intervention, regardless of attribution.

This includes the following:

AEs not previously observed in the patient that emerge during carfilzomib therapy (days 1through 16, and 28, 42, 90), including signs or symptoms associated with AMR that were not present prior to the AE reporting period.

Complications that occur as a result of protocol-mandated interventions.

AEs that occur prior to the assignment of study treatment that are related to a protocol-mandated intervention.

Preexisting conditions judged by the investigators to have worsened in severity or frequency or changed in character during carfilzomib therapy (days 1through 16, and 28, 42, 90).

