6.2.1 Adverse event reporting period

After informed consent is obtained but before any administration of study drug, only SAEs due to protocol mandated interventions will be recorded. Any AE or SAE at any time after the first infusion of carfilzomib is initiated until day 16, and on days 28, 42, 90 ±14 days must be recorded by the investigators and reported to Amgen as defined in this section. After this period, only SAEs deemed to be related to study drug will be recorded and reported.

Serious Adverse Event Reporting Contact Information:

Amgen Global Safety

Toll-free #:[name]

For countries where the U.S. toll-free # cannot be used: [contact]

Email (Only for sponsors with a secure email connection with Amgen):

[contact]

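### Two safety incidences (AEs requiring dose modification, SIRS) are counted over days 1-16 only, although a second in-study carfilzomib cycle is permitted

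*Combined protocol and SAP*

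**What the plan says.** **Treatment.** Section 5.3.1.1 says "Carfilzomib may be administered for 1-2 complete cycles in the study". Each cycle is six doses, on days 1, 2, 8, 9, 15 and 16. The second cycle is for patients who have not improved or who have regressed, and they must still meet the enrollment criteria (also section 5.1.2). No earliest or latest start day is given.

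**The two outcomes.** Section 4.4.3.2 reads "Incidence of adverse effects (AE) requiring dose-modification (see section 5.3.1.2) any time during days 1-16". Section 4.4.3.6 reads "Diagnosis of systemic inflammatory response syndrome (SIRS) any time during days 1-16". The synopsis (1.3) gives the same windows, for example "Incidence of adverse effects (AE) requiring dose-modification any time during days 1-16". The other five outcomes in 4.4.3 run at any time after day 1.

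**The clock.** Section 6.2.1 has AEs occurring "after the first infusion of carfilzomib is initiated until day 16, and on days 28, 42, 90 ±14 days must be recorded". Section 6.1.2 speaks of AEs that "emerge during carfilzomib therapy (days 1through 16, and 28, 42, 90". Appendices A and B put days 1-16, 28, 42 and 90 on one row. Section 5.3.1.1 counts its 90-day limit on a third cycle from the first cycle's day 1.

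**Reporting.** Section 5.13.1: "Study drug administration data will be listed by dose level, and any dose modifications will be flagged". Section 5.13.2: "All AE data will be listed by patient, cycle, and dose". Appendix B schedules the carfilzomib dose field, and the field for any other dose and its reason, only on the six cycle-1 dosing days.

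**The concern.** The regimen under test can run to two cycles, but the window for these two outcomes is exactly one cycle long. A dose reduction or a SIRS episode in a second cycle would not count in either incidence as written. The patients concerned have the greatest exposure, because they are planned to receive twice the doses.

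Section 4.1 says the results are needed for planning larger controlled trials. Someone using these two figures as the tolerability of the one-to-two-cycle regimen would take figures that describe cycle 1 only. To recover the cycle-2 part they would have to rebuild it from listings, and for cycle 2 the data-collection schedule has no dose or reason field.

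**Working it through.** **Inputs.** Dosing days 1, 2, 8, 9, 15 and 16 per cycle and a maximum of two cycles (5.3.1.1). Outcome window days 1-16 (4.4.3.2, 4.4.3.6). Visits at days 28, 42 and 90, each ±14 days (6.2.1). Planned enrollment 30, which section 5.13.3 bases on 10 per year × 3 years = 30. The 30 is used below only as a denominator. The plan gives no re-treatment rate and no per-cycle event rate.

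**Step 1: where cycle-2 doses fall.** If cycle 2 starts on study day s, dose day = s − 1 + d, with d = 1, 2, 8, 9, 15, 16. The last cycle-1 dose is on day 16, so s is at least 17.

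| Start s | Cycle-2 dose days | Inside days 1-16 |
|---|---|---|
| 17 | 17, 18, 24, 25, 31, 32 | 0 of 6 |
| 28 | 28, 29, 35, 36, 42, 43 | 0 of 6 |
| 42 | 42, 43, 49, 50, 56, 57 | 0 of 6 |
| 75 | 75, 76, 82, 83, 89, 90 | 0 of 6 |

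A re-treated patient has 12 planned doses, and 6/12 = 50% lie outside the window whatever the start day.

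**Step 2: share of all planned doses.** With k of 30 patients re-treated (assumed), the share outside is 6k/(180 + 6k):
- k = 3: 18/198 = 9.1%
- k = 6: 36/216 = 16.7%
- k = 9: 54/234 = 23.1%

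**Step 3: what that could do to an incidence.** This is illustrative only. Let p be the risk of at least one event per cycle, equal in both cycles and independent between them, and f the fraction re-treated. The day 1-16 incidence is p. The any-cycle incidence is p + f(1 − p)p. With p = 20%:
- f = 10%: 21.6%
- f = 30%: 24.8%
- f = 50%: 28.0%

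In patients of 30, that is 6.0 counted against 6.5, 7.4 and 8.4. Over p = 10-30% and f = 10-50% the gap f(1 − p)p runs from 0.1 × 0.9 × 0.1 = 0.9 points to 0.5 × 0.7 × 0.3 = 10.5 points. All values of p and f are assumptions.

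**Step 4: does the data schedule fill the gap?** The visit windows are days 14-42, 28-56 and 76-104, so days 57-75 lie in none of them. Appendix B has daily white-cell counts only through day 16, and the white-cell count is one of the four SIRS criteria. Section 6.3.3 records a laboratory abnormality only if it is clinically significant and needs active management. A cycle-2 SIRS count would therefore depend largely on the diagnosis having been entered as an AE.

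**Step 5: which clock?** Section 5.4 describes days 28, 42 and 90 as 2, 4 and 10 weeks after therapy ends. From day 16 the gaps are 12, 26 and 74 days, which fits a one-cycle patient. For a re-treated patient that description and a clock running from the first infusion cannot both hold.

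**The case against.** The strongest reply is that the day numbers may be meant per cycle. The only dosing schedule is days 1, 2, 8, 9, 15 and 16, so those numbers must restart for a second cycle. Section 5.3.1.1 refers to day 1 of the first cycle, which implies another day 1. Section 5.4 ties the later visits to the end of therapy. This stands as a possible reading, so it goes too far to say that the plan plainly excludes cycle-2 events. But no text applies the restart to the outcome windows, and sections 6.1.2 and 6.2.1, the appendices and the 90-day rule point to one clock. Either way, the text needs a sentence.

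Second, much of the cycle-2 safety information is collected anyway. The any-AE outcome has no day-16 limit, AEs are listed by cycle, dose modifications are flagged, and section 6.2.3 has investigators ask about AEs at every contact. Study therapy is inpatient (5.4), and section 7.7 requires drug-dispensing records. This also stands. A reader might infer that cycle-2 safety data are lost, and the documents do not support that.

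Third, a cycle-1 window gives every patient the same planned exposure. That is a good reason to report a cycle-1 figure, but not to report only that one.

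A reader might also infer that the day-42 and day-90 DSA and FEV1 results are biased because they mix one-cycle and re-treated patients. The documents do not support this. The regimen is one to two cycles, and the observed values describe it. Section 4.4.2.1 calls the day-42-to-90 quantity an absolute change and does not claim durability. A split by re-treatment would help interpretation, but it would not correct an error.

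**Conclusion.** The point holds in a limited form. On the clock that the documents best support, the dose-modification and SIRS incidences cover cycle 1 only, while the permitted regimen is one or two cycles. Half of each re-treated patient's planned doses fall outside. As estimates for the permitted regimen, both patient-level incidences can only be too low or unchanged, never too high.

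The size in events cannot be derived. It depends on how many patients are re-treated and on their cycle-2 risk, and the plan gives neither. The 9.1-23.1% dose shares rest on an assumed 3 to 9 re-treated patients. The 0.9-10.5 point range adds assumed, equal and independent per-cycle risks. If nobody is re-treated, or if per-cycle windows were intended and applied, the numbers do not change and only the wording needs repair.

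**What to change.** 1. In 4.4.3.2, 4.4.3.6 and the synopsis, define the window as *days 1-16 of each cycle*.
2. Report both incidences for cycle 1, for cycle 2 (among re-treated patients) and overall. The cycle-1 figure keeps the equal-exposure comparison.
3. Repeat the Appendix B dose, dose-modification, laboratory and AE fields for cycle 2.
4. State that days 28, 42 and 90 count from day 1 of the first cycle, and limit the weeks-after-therapy description in 5.4 to one-cycle patients.

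Optional and descriptive only: tabulate day-42 and day-90 DSA and FEV1 by whether and when a second cycle was given.

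The cost is a few lines of wording, one repeated set of fields and some additional data entry. Eligibility for a second cycle does not change. The reported rates of both outcomes may rise.
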